17.3.1. LABORATORY REFERENCE RANGES

Quantitative laboratory measurements will be compared with the relevant laboratory reference ranges by the lab vendors and categorized as:

- Low: Below the lower limit of the laboratory reference range.
- Normal: Within the laboratory reference range (upper and lower limit included).
- High: Above the upper limit of the laboratory reference range.

Clinical laboratory reference/normal ranges will be listed.

17.4. ECG EVALUATIONS

Results of the ECG assessments will be included in the reporting of this study.

Overall interpretation of ECG will be summarized for the following categories:

- 0 Normal
- Abnormal, Not Clinically Significant (ANCS) 0
- Abnormal, Clinically Significant (ACS)

Number and percent of subjects for each category will be presented by dose levels and schedule assessment visit/day.

The following summary will be provided for 12-lead ECG parameters PQ interval (PR), RR interval (RR), QRS interval (QRS), QT interval (QT), QTc interval (QTcF) and Heart Rate (HR) based on the Safety Population.

Actual and change from baseline by dose levels and scheduled assessment visit/day for SAD and MAD study part

All ECG assessments will be listed for each study part.

Document: CALIBR CBR-KA34-3001 SAP Final 1.0

Author: PPD Version Number: Version Date:

Final 1.0 15MAY2020

Template No: CC Effective Date: 01Apr2016 Reference:

17.5. VITAL SIGNS

The following Vital Signs measurements will be reported for SAD and MAD study part of this study:

- Systolic and Diastolic Blood Pressure (mmHg)
- Pulse Rate (bpm)
- Temperature (°C)

For each study part, the following summaries will be provided for vital signs data based on the Safety Population:

Descriptive statistics summary for observed and change from baseline by dose levels, scheduled assessment visit/day and timepoint as appropriate

All vital signs data will be listed for each study part.

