| ALLOWABLE VISIT WINDOW           | -28 to -1 days |                           |     | -/- 2     | +/ <del>-</del>       | -/-       | -/+       | -/+      | -/+      |                       | -
1                | + 1                               | - <del>-</del>              | +/-       | + %                    | -/+   | 30                        |
|                                  | ,              |                           |     | Min       | Min                   | Min       | Min       | Min      | Min      |                       | Day L I    | Day L Day L | $\mathrm{Day}^{\mathrm{L}}$ | Day       | Days                   | Days  | Days                      |
| Adverse Events H      |                |                           | X   | X         | X                     | X         | X         | X        | ×        | X                     | X                     | X                                 | ×                           | X         | X                      | ×   | X                         |
| Contraception Review             | X              |                           |     |           |                       |           |           |          | X        | X                     | X                     | X                                 | X                           | X         |                        |   |                           |

A Day 2 and Day 50 Visits may be conducted via telephone

B Vital signs (temperature, seated blood pressure, and pulse rate) should be collected pre-dose and 30 minutes after dosing on Days 8, 15, and 22

C Tibial-femoral x-rays to confirm the diagnosis of OA and Kellgren & Lawrence Grade must be of acceptable quality and acquired within 6 months prior to Screening

D Safety laboratory testing includes hematology, chemistry, and urinalysis; will be performed at the site's laboratory

E For female subjects; will be performed at the site's laboratory

F The WOMAC should be administered at the beginning of the visit prior to completing other procedures

G Optional banked biospecimen collection

H Adverse Events are captured starting at time of consent. Any Adverse Events during Screening and Day 1 will be captured and noted as part of medical history

Screening procedures may be completed across multiple days during the 28 day screening period and do not need to be conducted on consecutive days

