#### 6.3.3. Day 8 (Visit 4)

The following procedures will be completed on Day 8:

- Collect blood and urine samples for safety laboratory tests
- Collect pre-dose blood sample for PK analysis
- Collect pre-dose serum sample for PIIANP assessment
- Collect pre-dose urine sample for CTX-II assessment
- Collect pre-dose serum sample for biospecimen banking (if the subject has consented to provide this optional sample)
- Administer the WOMAC
- Record any changes in concomitant medications

- Conduct targeted physical examination
- Obtain weight
- Obtain pre-dose temperature and seated BP and PR
- Obtain 12-lead ECG
- Collect pre-dose synovial fluid sample for biospecimen banking (if the subject has consented to provide this optional sample)
- Administer KA34 or placebo
- Obtain temperature and seated BP and PR 30 minutes after dosing (+/- 5 minute window)
- Assess adverse events by spontaneous reporting and by asking the subject to respond to a non-leading question such as "How do you feel?"
- Remind the subject about study contraception requirements and confirm highly effective contraception is being used (if applicable)

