### 6.3.5. Day 22 (Visit 6)

The following procedures will be completed on Day 22:

- Collect pre-dose blood sample for PK analysis
- Collect pre-dose serum sample for PIIANP assessment
- Collect pre-dose urine sample for CTX-II assessment
- Collect pre-dose serum sample for biospecimen banking (if the subject has consented to provide this optional sample)
- Record any changes in concomitant medications
- Obtain weight
- Obtain temperature and seated BP and PR
- Collect pre-dose synovial fluid sample for biospecimen banking (if the subject has consented to provide this optional sample)
- Administer KA34 or placebo
- Collect temperature and seated BP and PR 30 minutes after dosing (+/- 5 minute window)
- Assess adverse events by spontaneous reporting and by asking the subject to respond to a non-leading question such as "How do you feel?"
- Remind the subject about study contraception requirements and confirm highly effective contraception is being used (if applicable)
- Subjects may be discharged after at least 2 hours of safety observation following the last procedure

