## 7.1.4. Vital Signs

Temperature, blood pressure (BP), and pulse rate (PR) will be measured at times specified in the Schedule of Activities and Study Procedures section of this protocol.

Temperature should be measured orally.

Seated BP should be measured with the subject's feet flat on the floor and back supported and the subject's arm supported at the level of the heart. BP should be recorded to the nearest mm Hg after at least 5 minutes of rest. Subjects should be instructed not to speak during measurements. A properly sized and calibrated BP cuff should be used for each measurement. PR will be measured in the brachial/radial artery for at least 30 seconds. The use of an automated device for measuring BP and PR is acceptable. When the timing of these measurements coincides with a blood collection, BP and PR should be obtained prior to the nominal time of the blood collection with the exception of Screening and Pre-Dose.

On Day 1, vital signs will be measured pre-dose and at 15 minutes, 30 minutes, 60 minutes, 90 minutes, 2 hours, and 4 hours after dosing for all subjects (+/- 5 minutes). For subjects in the multiple dose cohorts, vital signs will be measured pre-dose and 30 minutes post-dosing (+/- 5 minute window) on Day 8, Day 15, and Day 22.

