6.5. BASELINE

Baseline, is defined as the last scheduled non-missing measurement taken prior to the first dose.

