6.7. COMMON CALCULATIONS

For quantitative measurements, change and percent change (as appropriate) from baseline will be calculated as:

- Change from baseline = Post baseline Value baseline Value, if baseline is not missing.
- Percent change from baseline = 100*[(Post baseline Value baseline Value)/baseline Value], if baseline if not missing.

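### Does measuring the 30-minute vital-sign change at multiple-dose injections 2 to 4 only against the pre-first-dose baseline leave the safety summary deficient?

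*SAP*

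**What the plan says.** SAP 17.5 reports systolic and diastolic pressure, pulse rate and temperature for each study part as a "Descriptive statistics summary for observed and change from baseline by dose levels, scheduled assessment visit/day and timepoint as appropriate". It adds: "All vital signs data will be listed for each study part". Under SAP 6.5, baseline "is defined as the last scheduled non-missing measurement taken prior to the first dose", and no section resets it for later injections. SAP 6.7 defines the change as the later value minus that single baseline: "Change from baseline = Post baseline Value baseline Value, if baseline is not missing" (the minus sign is lost in the extracted text).

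On collection, the footnote on vital signs in the multiple-dose Schedule of Activities says they "should be collected pre-dose and 30 minutes after dosing on Days 8, 15, and 22". Protocol 7.1.4 agrees: "vital signs will be measured pre-dose and 30 minutes post-dosing (+/- 5 minute window) on Day 8, Day 15, and Day 22". The visit lists in Protocol 6.3.3 and 6.3.5 carry the same post-dose reading ("Obtain temperature and seated BP and PR 30 minutes after dosing (+/- 5 minute window"; "Collect temperature and seated BP and PR 30 minutes after dosing (+/- 5 minute window").

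Protocol 2.4 and SAP 2.2.1 name change from baseline in vital signs as a secondary endpoint. Neither names a change per injection.

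**The concern.** A same-day pair of readings is taken at injections 2, 3 and 4, yet the SAP text does not describe subtracting one from the other. The 30-minute change on those days therefore mixes any response to the injection with whatever has drifted since Day 1. On Day 1 the problem does not arise, because the reference is normally taken within 2 hours before dosing.

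The protocol also gives a reason to look at that interval. Section 1.2.1 reports a transient systolic fall of 14 and 15 mmHg at 0.5 hours in an intravenous dog study, and says vital signs will be monitored before and after dosing. If the planned tables hid an acute fall after repeat injections, a descriptive safety analysis would miss what that monitoring is meant to detect.

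**Working it through.** **1. Age of the reference value.** Days 8, 15 and 22 have a window of ±1 day, with at least 7 days between injections (multiple-dose Schedule of Activities). The baseline is then 7–8, 14–15 or 21–22 days old. This part of the concern is correct.

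**2. Number of pairs.** Each of the three multiple-dose cohorts has 9 active and 3 placebo subjects (SAP 3.1). Active: 27 × 3 days = 81 pairs. Placebo: 9 × 3 = 27. The total is 108 if nothing is missed. A table by day has 9 active subjects per dose level, because the three days repeat the same people.

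**3. What the planned table already yields.** With complete pairs,

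mean(post − pre) = mean(post − Day 1) − mean(pre − Day 1).

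Both terms on the right come from SAP 17.5. Suppose every subject is 14 mmHg above baseline before dosing and falls 14 mmHg by 30 minutes. The 30-minute row shows 0, the pre-dose row shows +14, and 0 − 14 = −14. At group level the fall is visible.

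**4. What it does not yield.** Two constructed data sets of 9 subjects each have the same planned change-from-baseline summary: pre-dose mean 0, SD 8.2; post-dose mean −5, SD 8.2. In one, every same-day change is −5 (SD 0). In the other, the same-day SD is 16.4 and the range is −29 to +19. So the paired SD, minimum and maximum cannot be rebuilt from the table, and neither in general can the median. The individual changes can be worked out from the listing.

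**5. Size of the loss, on assumed SDs.** The documents give no blood-pressure SD or correlation. Let b be the visit-to-visit SD and w the within-visit SD:

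- SD of change from Day 1 = √[2(b² + w²)]
- SD of same-day change = √2 × w

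| b, w (mmHg) | From Day 1 | Same day | Reduction |
|---|---|---|---|
| 0, any w | √2 × w | √2 × w | 0% |
| 4, 8 | 12.6 | 11.3 | 11% |
| 8, 6 | 14.1 | 8.5 | 40% |
| 12, 4 | 17.9 | 5.7 | 68% |

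The alternative form is SD × √[2(1 − ρ)], with between-visit ρ of 0.5–0.7 and same-day ρ of 0.7–0.8. The ratio of the two SDs is then √[(1 − ρ between)/(1 − ρ same day)]. It runs from √(0.3/0.3) = 1.00 to √(0.5/0.2) = 1.58, a reduction of 0% to 37%.

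The 68% corner is implausible. With an observed SD of 15 mmHg, b = 12 and w = 4 imply a between-visit correlation of 1 − (144 + 16)/225 = 0.29. The gain depends on the assumption chosen and can be nil.

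**6. What relies on the missing statistics.** Protocol 9.5 rules out formal safety tests. SAP 4.1 places DSMB reporting outside the SAP. Abnormal readings that meet the Protocol 8.2.2 conditions become adverse events, and clinically significant vital-sign abnormalities enter the pause rule in Protocol 3.2. None of these uses the spread of the same-day change.

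**The case for a change.** The best argument for a same-day table is about individuals. A mean recovered by subtraction shows neither spread nor extremes. The shared placebo reference protects against bias from drift but does not remove the added scatter. At b = 8 and w = 6, with no drug effect, the expected minimum-to-maximum span for 9 subjects is 2.97 SDs: 42.0 mmHg against Day 1 and 25.2 mmHg against the same-day reading. An individual fall of about 15 mmHg would be easier to notice in the second. Thirty minutes is the only post-dose vital-sign time kept at injections 2 to 4, and reading up to 108 pairs from a listing is tedious. The extra table would need no new data.

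All of that stands as a case for convenience. It does not show a fault:

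- The dog finding came at exposures the protocol describes as far above those expected from joint injection. The protocol's response was to monitor before and after dosing, which collection and listing do.
- Day 1 already gives the within-visit change at six post-dose times. SAP 15.1 expects no quantifiable parent drug in plasma beyond 4 hours, so little systemic carry-over is expected at later injections.
- SAP 8 leaves the format and content of the tables to shells that are not in the text available here. A same-day column may already be there.

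**Conclusion.** The concern does not hold. The SAP applies one consistent baseline, that baseline answers the stated endpoint, and it is the right reference for cumulative change over the four injections. Followed as written, the plan shows drift in the pre-dose rows, allows the mean same-day change to be derived when pairs are complete, and lists every reading.

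What the text does not describe is limited to four descriptive statistics of the same-day change, on about 9 active subjects per dose level on each of three days. Adding them would change no planned result or conclusion. Any benefit in mmHg rests wholly on assumed SDs and ranges from none to substantial.

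This conclusion assumes that the pre-dose and 30-minute readings on Days 8, 15 and 22 are tabulated as separate timepoints, as SAP 17.5 indicates. The mean comparison also assumes few incomplete pairs. A same-day summary is an optional extra, and the plan needs no change.

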17.6. PHYSICAL EXAMINATION

Physical exam results will be listed including specification of any abnormalities observed for each study part.

18. **EXPLORATORY ANALYSIS**

18.1. WESTERN ONTARIO AND McMaster Universities Osteoarthritis Index (WOMAC)

The WOMAC is a validated, patient self-report measure that assesses the dimensions of pain, stiffness and physical function in patients with OA of the hip or knee. In this study the WOMAC will use the 100 mm visual analogue scale (VAS) format.

The WOMAC consists of 24 items divided into 3 subscales:

- Pain (5 items): while walking, using stairs, in bed, sitting or lying, and standing
- Stiffness (2 items): after first waking and later in the day
- Physical Function (17 items): stair use (descending and ascending), rising from sitting, standing, bending, walking, getting in/out of a car, shopping, putting on socks, taking off

CALIBR_CBR-KA34-3001_SAP_Final 1.0 Document: Author: Version Number: Final 1.0 PPD 15MAY2020 Version Date: Template No: CC Reference: CC Effective Date: 01Apr2016

Copyright © 2017 IQVIA. All Rights Reserved.

socks, rising from bed, lying in bed, getting in/out of bath, sitting, getting on/off toilet, heavy household duties, light household duties

The patient's response to each question produces a score that is then summed to derive an aggregated score for each subscale. The total WOMAC score (WOMAC index) provides a measure of overall disability.

Actual and change from baseline of the WOMAC total score and the WOMAC pain and function subscale scores will be presented by dose levels and visit for SAD and MAD study part.

WOMAC scores will be listed for SAD and MAD study part.

18.2. WHOLE-ORGAN MAGNETIC RESONANCE IMAGING SCORE (WORMS)

WORMS is a semi-quantitative scoring method for multi-feature, whole organ evaluation of the knee in OA using conventional MR images. A trained evaluator will review the MRIs and determine a Whole-Organ Magnetic Resonance Imaging Score (WORMS). This will be assessed at Screening visit for SAD part and Screening, Day 90 and Day 180 visits for MAD part of the study.

Actual and Change from baseline in Total Whole-Organ Magnetic Resonance Imaging Score (WORMS) of the index knee will be presented by dose levels and visit for MAD study part.

WORMS will be listed for SAD and MAD study part. Scores by category, scores by joint regions and total scores will be listed for each subject.

19. Data Not Summarized or Presented

The other domains not summarized or presented are:

Comments

These domains will not be summarized or presented, but will be available in the clinical study database, SDTM and/or ADaM datasets.

Document: CALIBR_CBR-KA34-3001_SAP_Final 1.0
Author: PPD

hor: PPD Version Number: Version Date:

Reference: CCI

Final 1.0

15MAY2020

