#### 2.5. Exploratory Objectives

- To assess changes in cartilage and osteoarthritis symptoms after administration of KA34
- To collect and bank biospecimen samples for exploratory biomarker research

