# 7.5.2. Magnetic Resonance Imaging (MRI)

MR images of the index knee will be acquired during Screening for all subjects. Subjects in the multiple-ascending dose cohorts will also have post-treatment MR images collected on Day 90 and Day 180 to support exploratory analyses of structural changes to the knee after

administration of KA34. A trained evaluator will review the MRIs and determine a Whole-Organ Magnetic Resonance Imaging Score (WORMS). WORMS is a semi-quantitative scoring method for multi-feature, whole organ evaluation of the knee in OA using conventional MR images (Peterfy, et al., 2002). Alternative semi-quantitative scoring methods to grade cartilage pathology with MRI such as the Knee Osteoarthritis Scoring System (KOSS) or the Boston-Leeds Osteoarthritis Knee Score (BLOKS) may also be used. Details of the MRI procedures will be provided in the Imaging Manual.

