# 9.4. Pharmacodynamic Analyses

The pharmacodynamics of KA34 will be evaluated by examining several exploratory endpoints, including biomarker data from PIIANP and CTX-II, clinical symptoms as assessed by the WOMAC, and imaging data. The pre-treatment values for these endpoints will be compared to post-treatment measurement and both the absolute and percent change from baseline will be summarized. Descriptive statistics for PD endpoints by time point and by treatment group will include number of observations, arithmetic mean, standard deviation, arithmetic coefficient of variation (%CV), median, minimum, and maximum. An exploratory analysis of PK/PD endpoints may also be performed.

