6.1. SUMMARY STATISTICS

For qualitative variables, the population size (N for sample size and n for available data) and the percentage (of available data) for each class of the variable will be presented. Quantitative variables of safety and PD data will be summarized using descriptive statistics, including N, mean, standard deviation (SD), arithmetic coefficient of variation (CV%) as appropriate, median, minimum, and maximum values. Geometric mean and geometric CV% will be included for PK parameter summaries. CV% will not be presented for change from baseline results.

Results will be summarized if n is greater than or equal to 2 per group and otherwise reported as N/A (ie, Not Applicable).

Document: CALIBR_CBR-KA34-3001_SAP_Final 1.0
Author: PPD Version Number: Final 1.0
Version Date: 15MAY2020

Template No: CE Reference: CE

Copyright © 2017 IQVIA. All Rights Reserved.

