16. PHARMACODYNAMIC ANALYSIS

16.1. PHARMACODYNAMIC ASSESSMENTS

The pharmacodynamics of KA34 will be evaluated by examining several exploratory endpoints, including biomarker data from serum levels of the N-propeptide of type IIA collagen (PIIANP) and urinary excretion of C-terminal cross-linking telopeptide of type II collagen (CTX-II).

Clinical symptoms as assessed by the Western Ontario and McMaster Universities Osteoarthritis Index (WOMAC) Version 3.1 total score and the WOMAC pain and function subscale scores, and Tibial-femoral radiographs imaging data are exploratory, see Section 18.

The pre-treatment values for PIIANP and CTX-II endpoints will be compared to post-treatment measurements and both the absolute and percent change from baseline will be summarized. Descriptive statistics for PD endpoints by time point and by dose levels. An exploratory analysis of PK/PD endpoints may also be performed but is not planned.

A listing of PD sample collection times and subject listings of all PIIANP and CTX-II concentration-time data for each dose levels will be presented. Summary tables for both the observed values and the baseline-corrected values. Figures of mean baseline-corrected concentration-time data will be presented by each dose levels. Individual observed concentration-time data for each subject will be presented graphically.

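### Two exploratory summaries could be improved cheaply: no imaging table in the SAP body isolates cartilage, and the mean percent change in PIIANP and CTX-II is expected to be above zero when nothing changes

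*SAP*

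**What the plan says.** **Imaging.** Protocol 2.5 gives as an exploratory objective "To assess changes in cartilage and osteoarthritis symptoms after administration of KA34". The imaging endpoint in protocol 2.6 is change from baseline in WORMS of the index knee, with no sub-score named. Both documents describe WORMS as a multi-feature score of the whole knee. SAP 18.2 states the tabulation, which is also by visit and covers the multiple-dose (MAD) part: "Actual and Change from baseline in Total Whole-Organ Magnetic Resonance Imaging Score (WORMS) of the index knee will be presented by dose levels". It then adds: "Scores by category, scores by joint regions and total scores will be listed for each subject". SAP 10 places MRI and radiograph status in listings, and SAP 18 describes no other imaging table.

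**Markers.** For PIIANP and CTX-II, SAP 16.1 says that "both the absolute and percent change from baseline will be summarized". SAP 6.7 divides each subject's change by that subject's own baseline, and SAP 6.5 makes baseline one value, the last scheduled one before the first dose. Protocol 9.4 sets the statistics: "Descriptive statistics for PD endpoints by time point and by treatment group will include number of observations, arithmetic mean, standard deviation", followed by CV, median, minimum and maximum. SAP 6.1 plans mean, SD and median for PD data and reserves geometric means for PK parameters. SAP 6.2 pools placebo subjects over dose levels.

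**The concern.** **Imaging.** KA34 is intended to promote cartilage repair. If cartilage responds and the other scored features mainly add variability, the total shows the response less clearly than the cartilage category would. A reader who wants the cartilage result by dose would have to assemble it from subject listings. SAP 18.1 already tabulates WOMAC pain and function beside the WOMAC total, so the plan accepts component tables elsewhere.

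**Markers.** A ratio with a noisy denominator has an expectation above one even when nothing changes. Protocol 9.4 plans a comparison of pre-treatment with post-treatment values, so the mean percent change will be read within groups. For PIIANP, a synthesis marker, the bias leans towards apparent activity. For CTX-II, a degradation marker, it hides part of a fall. In the MAD part the same baseline value serves Days 8, 15, 22, 29, 90 and 180, so its error is shared across visits and a spurious rise can look sustained.

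**Working it through.** The plan states no figure to reproduce here: no marker variability, no expected change and no power.

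**Direction of the marker bias.** Let X be the baseline and Y the later value, both positive and exchangeable when nothing changes. Then E[Y/X] = E[(Y/X + X/Y)/2]. Since r + 1/r is at least 2 for any positive r, the expectation is at least 1, and it exceeds 1 unless X and Y are always equal. The log ratio is symmetric about 0, so the population median ratio is 1. The direction needs no assumed CV or distribution.

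**Size.** Inputs: 9 active subjects per MAD cohort, and 3 or 6 per single-dose cohort (protocol 3.1). The within-subject CV is an assumption, since the documents give none; 10% to 40% is shown. With lognormal errors, s² = ln(1 + CV²).

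- Independent errors: expected mean percent change = 100 × (exp(s²) − 1) = 100 × CV².
- Log-scale error correlation 0.5: 100 × (√(1 + CV²) − 1).
- SE of the mean at n = 9, independent errors: √[(exp(2s²) − 1) × exp(2s²)] / 3. At CV 30%, exp(2s²) = 1.09² = 1.1881, so SE = √(0.1881 × 1.1881)/3 = 0.158.
- Average geometric mean ratio in a group of n: exp(s²/n). At CV 30% and n = 3, exp(0.0862/3) = 1.029.

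Probabilities and average medians come from simulating 400,000 groups per setting with no true change and independent errors.

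| Assumed CV | 10% | 20% | 30% | 40% |
|---|---|---|---|---|
| Expected mean, independent errors | +1.0% | +4.0% | +9.0% | +16.0% |
| Expected mean, error correlation 0.5 | +0.5% | +2.0% | +4.4% | +7.7% |
| SE of mean at n = 9 (points) | 4.8 | 9.9 | 15.8 | 22.7 |
| Bias / SE at n = 9 | 0.21 | 0.40 | 0.57 | 0.70 |
| Group mean above 0, n = 9 | 58% | 64% | 70% | 75% |
| Group mean above 0, n = 3 | 53% | 56% | 59% | 61% |
| Average group median, n = 9 | +0.2% | +0.7% | +1.4% | +2.5% |
| Average group median, n = 3 | +0.4% | +1.8% | +3.9% | +6.9% |
| Average geometric mean ratio, n = 3 | +0.3% | +1.3% | +2.9% | +5.1% |

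The group median is above 0 in 50% of groups at n = 3 and n = 9, and in about 51 to 52% at n = 6. The geometric mean ratio is above 1 in 50%. Gamma instead of lognormal errors give mean biases of +4.2% and +9.9% at CV 20% and 30%. Mean absolute change is 0 throughout.

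**A true 10% fall**, independent errors: 0.9 × (1 + CV²) − 1 = −9.1/−6.4/−1.9/+4.4% at CV 10/20/30/40%. With correlation 0.5 at CV 40% it is 0.9 × 1.077 − 1 = −3.1%.

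**Against placebo.** With equal CVs the biases are equal and the expected difference is 0. With pre-dose CV 20% in both arms, post-dose CV 30% or 40% on active only and an unchanged geometric mean, the difference is √(1.04 × 1.09) − 1.04 = 2.5 points or √(1.04 × 1.16) − 1.04 = 5.8 points. The SE of the difference is 16 or 19 points at 9 against 9. If the arithmetic mean is unchanged instead, the difference is 0.

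**WORMS.** No SDs are given, so this is illustration only. Suppose the other features are uncorrelated with cartilage and their change has k times its SD. If only cartilage responds, the total keeps 1/√(1 + k²) of the standardised effect: 89/71/45% at k = 0.5/1/2. If the other features respond with the same standardised effect, the factor is (1 + k)/√(1 + k²), which at k = 1 is 1.41. The total can therefore be less or more sensitive than the cartilage score.

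**The case against.** The strongest reply on imaging is that the SAP does what the protocol asks. The endpoint is WORMS without a sub-score, and protocol 7.5.2 gives the purpose of the post-treatment scans as exploratory analysis of structural change in the knee. A reader might infer from the phrase "Alternative semi-quantitative scoring methods to grade cartilage pathology with MRI" that MRI was meant to grade cartilage and that SAP 18.2 departs from this. The documents do not support that: the phrase describes the alternatives to WORMS, not WORMS or the scans. The category scores are listed, PIIANP and CTX-II also bear on cartilage and are tabulated, and SAP 8 refers to table shells that are not in the available text. All of this stands. What remains is a gap between the objective and the imaging tables described in the SAP body.

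On the markers, the reply is that protocol 9.4 itself requires the arithmetic mean and percent change, that median, absolute change and pooled placebo are all planned, and that the bias is below one SE in every case above. This also stands. A low CV or correlated errors shrink the bias, and the apparent rise despite a true 10% fall needs the 40% CV with independent errors. A reader might also infer that the median and the geometric mean ratio are free of bias. In small groups their averages are slightly positive too; at n = 3 and CV 30% they are about +4% and +3%, against +9% for the mean. Their advantage is that each falls above no change about half the time.

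**Conclusion.** Both parts hold as cheap improvements to exploratory, descriptive summaries.

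The imaging part is a missing table, not a contradiction or a breach of the endpoint, and is established only for the SAP body. Whether the total would hide a cartilage effect, and by how much, cannot be told from the documents.

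For the markers, the upward direction follows from the planned formula when baseline and post-dose values are exchangeable. The size rests on the assumed CV and error correlation: with independent errors, +1% to +16% over CVs of 10% to 40%, or 0.2 to 0.7 SE at n = 9, with the cohort mean positive in 58 to 75% of cases. Correlation 0.5 roughly halves the bias. A reader might infer that it creates a false difference from placebo. With similar variability in the arms it largely cancels, so the point concerns only the within-group reading of the mean percent change.

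**What to change.** 1. **SAP 18.2.** Keep the total WORMS table and add one for the MAD part, by dose level and visit, showing observed values and change from baseline in the cartilage category score(s) already captured for the listing. Name the category or categories used; the protocol and SAP do not.

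2. **SAP 16.1.** For PIIANP and CTX-II, add the geometric mean ratio to baseline, analysed on the log scale and shown as a percent, by dose level, pooled placebo and time point. State that this and the median are the percent-change summaries to interpret. Keep every statistic named in protocol 9.4. A rule for values below quantitation is needed only if such values occur.

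The cost is SAP wording and programming, with one more table and one more statistic. No new data are needed, and protocol 9 allows the SAP to modify the outlined analyses where appropriate.
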